3.0 Secondary Analyses

All secondary analyses will be performed separately for each of the two primary cohorts. The analyses below will follow the guidelines outlined in section 2.2. Secondary analyses will be considered significant if the p-value is less than 0.01.

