1 **Hyperopia Treatment Study (HTS1)**
 2 **Immediate versus Delayed Treatment In Children with Moderate**
 3 **Hyperopia**

4
 5 **Statistical Analysis Plan**
 6 **Version 3.0**

7
 8
 9
 10 Statistical Analysis Plan Version: 3.0, 25Jul18
 11 Protocol Version: 3.0, 28Jan15

12
 13
 14 **VERSION HISTORY**

The following table outlines changes for the analysis plan:

VERSION NUMBER	AUTHOR	APPROVER	EFFECTIVE DATE	REVISION DESCRIPTION*
1.0	[name]	[name]	12-19-17	Initial draft written after study was completed but before manuscript was written.
2.0*	[name]	[name]	05-14-18	Lead authors decided to redefine “best” stereoacuity and visual acuity at the 3-year outcome visit to be consistent with what was done for the IXT study. When preparing to unmask the study investigators to the results, the leads realized that it was not our intent to compare deterioration rates between the two groups. In the planning phase, the planning committee felt the deterioration rates in each group would aid in interpreting the results. The committee felt a formal statistical comparison was not needed because the rate of deterioration was expected to be higher in the observation group than in the glasses group.
3.0*	[name]	[name]	07-27-18	Lead authors decided to redefine best stereoacuity and best visual acuity at the 3-year outcome visit as the best of measurements reported with and without trial frames, during the initial assessment and retest, if required. During their final review of the manuscript, the leads realized that results reported for primary and secondary analyses were discordant. The leads determined that the definitions of best stereoacuity and best visual acuity needed updating to reflect the study design and to be in concordance with results reported in the primary analysis.

* indicate in the description if the changes were made after review of outcome data

15 **1.0 Primary Objective**

16 The primary study objective is to compare visual outcomes and development of strabismus after a
17 36-month follow-up period in two age cohorts (children age 12 to <36 months and children age
18 36 to <72 months) with moderate hyperopia (spherical equivalent +3.00D to +6.00D in either
19 eye) who are prescribed glasses either immediately or only after pre-specified deterioration
20 criteria are met.

21
22 **2.0 Primary Analysis**

23 The primary analysis will be a treatment group comparison of the proportion meeting failure

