63 Failure criterion must be confirmed by a retest both with and without correction to be considered
64 a failure.

66 If failure is confirmed and the subject requires a change in glasses (*section 4.3* of the protocol),
67 the 36-month outcome exam is repeated on a different day 4 weeks \pm 1 week later (subsequently
68 referred to as the 37-month visit) by the masked examiner with the child wearing their new
69 glasses. Testing without correction does NOT need to be repeated. Failure will be assessed at this
70 post-36 month exam, and the subject will be classified as a failure if he/she meets any of the
71 failure criteria above. If the subject meets any failure criteria (with the exception of strabismus
72 surgery), the visual condition that is considered to be failed must be retested by the masked
73 examiner using the same procedures outlined above. Failure must be confirmed without
74 correction at the 36-month exam and with correction at this repeat outcome exam 4 weeks later to
75 be considered a failure.

77 **2.2 Principles to be Followed in Primary Analysis**

78 The following principles apply to the primary treatment comparison:

- 79 1. The primary treatment comparisons will be performed using a modified “intent-to-treat”
80 analysis principle. The data of all randomized subjects completing the 36-month exam
81 will be included in the analysis regardless of whether the assigned treatment was actually
82 received. Data from subjects who receive alternate treatment (i.e. glasses for subjects
83 assigned to observation who did not meet deterioration criteria and vice versa) will be
84 analyzed according to randomization group. There will be no imputation of data for
85 subjects who are lost to follow-up or withdrawn from study prior to the primary outcome,
86 defined as the failure status at the 36-month visit if the 37-month visit is not required and
87 failure status at the 37-month visit if required.
- 88 2. Subjects who meet failure criteria at the 36-month assessment and have significant
89 changes in their cycloplegic refraction are prescribed glasses and required to return
90 within 4 weeks to be retested in their updated correction. If this happens, the results of the
91 36-month examination without correction and the 37-month examination with correction
92 will be used to determine failure status in the primary analysis.
- 93 3. Subjects will be included in analysis as long as the 36-month visit was completed. Seeing

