94 as failure must be confirmed, subjects who complete the 36-month visit will not be
95 considered to have met failure criteria for a condition if a required test or retest was not
96 performed.
- 97 4. Data will be considered missing if not completed within the analysis window. The 36-
98 month assessment must be completed no earlier than 33 months (1005 days) and no later
99 than 42 months (1282 days). Subjects will be excluded from analysis if the 36-month
100 visit is not completed within the analysis window.
- 101 5. The 37-month visit is an extension of the 36-month visit. No analysis window is defined
102 for the 37-month visit. If required and collected, data at the 37-month visit will be used in
103 analysis. Subjects will be included in analysis if the 36-month visit was completed within
104 the analysis window. See Table 1 and Figure 1 below for clarification.
- 105 6. Imbalances between groups in important covariates measured at baseline are not expected
106 to be of sufficient magnitude to produce confounding. However, as a complement to the
107 primary analysis, the presence of confounding will be evaluated by including in the
108 model factors that appear to be imbalanced between treatment groups and are associated
109 with visual acuity, stereoacuity, or strabismus.

110
111 Barnard’s exact test does not allow for the adjustment of covariates. Binomial regression was
112 used to compare treatment groups when the model was adjusted for possible confounders.

Table 1: Analysis of Data based on Visit Completion

36-Month Visit			37-Month Visit Required	37-Month Visit Completed	Primary and Secondary Analyses ^a	Additional Approaches to Primary Analysis (Imputation) ^b
In Window	Out of Window	Not Completed				
-	-	X	-	-	Excluded	Impute
X			No	-	Data included	Data included
X			Yes	Yes	Data included	Data included
X			Yes	No	Data included	Impute
	X		No	-	Excluded	Impute
	X		Yes	Yes	Excluded	Impute
	X		Yes	No	Excluded	Impute

X indicates when visit was completed

-Visits are considered completed if data was collected at the visit. Completion status is not dependent on the amount of data collected at the visit.

[figure not shown]
^aSubjects will be included in the primary and secondary analyses as long as the 36-month visit was completed. Seeing as failure must be confirmed, subjects who complete the 36-month visit will not be considered to have met failure criteria for a condition if a required test or retest was not performed.

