2.4 Multiple Imputation

Multiple imputation using logistic regression will be used to impute 36-month failure status and will be performed separately for each primary cohort. Imputation in each cohort will be based on the presence of deterioration prior to 3 years and will be stratified by treatment group. The proportion of subjects who failed at 3 years will be tabulated for each imputed data set, and the results will be combined using the MiAnalyze procedure in SAS 9.4 to generate valid statistical inferences.

It is recognized that differential loss to follow up or a difference in the distribution of loss to follow-up times may introduce bias to the multiple imputation model. Prescribing or withholding treatment may influence a parent’s decision to keep their child enrolled in the study, therefore results may be subject to bias if subjects receiving one treatment regimen are more likely to withdraw from the study. Results may also be subject to bias if subjects in one treatment group tend to remain in the study longer than subjects in the other. Deterioration is identified during the

follow-up period, so the chance of meeting deterioration criteria increases with the number of completed visits.

The protocol states that the last-observation-carried-forward method would be used in addition to multiple imputation, but this is not possible as failure is only assessed at the 36-month visit.

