3.1 Deterioration in Observation and Glasses Groups

For each treatment group, the Kaplan-Meier estimate of the cumulative proportion of subjects meeting deterioration criteria will be calculated along with the corresponding confidence interval. The deterioration rate in the observation group is expected to be higher than that of the glasses group, so deterioration rates will not be compared between treatment groups.

For the purposes of this analysis, a visit is defined by its corresponding analysis window. If deterioration criteria were met at a visit other than one specified by the protocol, the analysis window in which the subject met deterioration criteria will be defined as the visit at which deterioration criteria were met.

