3.4 Presence of Strabismus at 36 Months

A treatment group comparison of the proportion of subjects who meet failure criteria for strabismus at 3 years, defined as having measureable heterotropia at distance, having measureable heterotropia at near, or having strabismus surgery prior to 3 years, will be performed using Barnard's exact test.

Once deterioration criteria are met, masked exams were waived for the remainder of the study, except for the 36 month exam. If a subject were to deteriorate due to poor stereoacuity or visual acuity, they would not be retested if measurable heterotropia was present at a subsequent exam. Hence it is not possible to determine whether strabismus failure criteria, which require a retest, were met at any subsequent exam other than the 36 month exam

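### SAP 3.0 and Table 1 apply the in-window 36-month-completer exclusion to every secondary analysis, and 3.1 makes no exception for its Kaplan-Meier deterioration estimate

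*SAP*

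**What the plan says.** - **Scope rule.** SAP 3.0 covers every analysis listed under it: "The analyses below will follow the guidelines outlined in section 2.2".
- **Content of that rule.** Section 2.2 item 1 limits the data to randomized subjects who complete the 36-month exam. Item 3 says "Subjects will be included in analysis as long as the 36-month visit was completed". Item 4 says "Data will be considered missing if not completed within the analysis window", sets the window at days 1005 to 1282, and excludes subjects whose 36-month visit falls outside it.
- **Table 1.** One column covers the primary and secondary analyses together. It shows exclusion in the row for a 36-month visit not completed and in all three rows for a visit out of window. Footnote a repeats the completion rule for both kinds of analysis.
- **Estimator.** Section 3.1, the first analysis under 3.0, says: "For each treatment group, the Kaplan-Meier estimate of the cumulative proportion of subjects meeting deterioration criteria will be calculated". Its only special rule assigns a deterioration to a visit window. It names no population, no censoring rule and no exception to 2.2.
- **Stated scope of 2.2.** That section opens with "The following principles apply to the primary treatment comparison".

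**The concern.** A Kaplan-Meier estimate is normally chosen so that children with incomplete follow-up count for as long as they were observed. A rule that keeps only children seen at 36 months removes the incomplete follow-up beforehand, and it does so by selecting on something that happens after most deteriorations.

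The 36-month visit is not needed to establish an earlier deterioration. Section 3.4 says "Once deterioration criteria are met, masked exams were waived for the remainder of the study", apart from the 36-month exam, so deterioration is settled when first met. Section 2.4 likewise treats it as identified during follow-up and uses it to impute failure for children without a 36-month outcome.

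Two competent analysts could therefore report different curves. One would follow 3.0 and Table 1 and drop the non-completers; the other would include everyone and censor. The version history (version 2.0) says the planning committee expected the deterioration rates in each group to help in interpreting the results, so the rates should have one definition.

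**Working it through.** **Step 1: the literal reading.** Section 3.1 falls under 3.0, 3.0 imports 2.2, and Table 1 states the exclusion for secondary analyses directly. Everyone who remains has a visit on or after day 1005. Almost nobody is then censored before the 36-month window, so the Kaplan-Meier estimate is close to (completers who deteriorated) / (all completers).

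**Step 2: when the two readings differ.** The SAP gives no deterioration rate, dropout rate or sample size, so there is no figure of its own to reproduce. For scale I used a six-visit life table in which every input is assumed:
- F = true 36-month deterioration; hazard per interval h = 1 − (1 − F)^(1/6).
- B, A = cumulative 36-month loss before and after deterioration; loss per interval b = 1 − (1 − B)^(1/6) and a = 1 − (1 − A)^(1/6).
- Event-free completers = (1 − F)(1 − B).
- Retained events = Σ over k = 1 to 6 of (1 − h)^(k−1) · h · (1 − b)^k · (1 − a)^(6−k).
- Completers-only estimate = retained events / (retained events + event-free completers).

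In this model, Kaplan-Meier in all randomized subjects with censoring returns F.

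Example, F = 40%, B = 10%, A = 40%: h = 0.0816, event-free completers = 0.60 × 0.90 = 0.540, retained events = 0.301, estimate = 0.301 / 0.841 = 35.8%.

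| Loss before / after event | Completers-only, true 40% | Completers-only, true 20% |
|---|---|---|
| 15% / 15% | 40.0% | 20.0% |
| 15% / 0% | 41.8% | 21.2% |
| 30% / 0% | 44.1% | 22.7% |
| 10% / 40% | 35.8% | 17.4% |

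Modest differences in loss, at true 40%: 10%/15% gives 39.4%, 10%/20% gives 38.7%, 15%/10% gives 40.6% and 20%/10% gives 41.3%. These are shifts of 0.6 to 1.3 points.

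**Step 3: data discarded, per 100 children at true 40%.**
- 15%/15%: 36.7 deteriorations are observed and 34.0 kept, so 2.7 (7.3%) are discarded; 12.3 event-free dropouts are removed instead of censored.
- 10%/40%: 37.8 are observed and 30.1 kept, so 7.7 (20.4%) are discarded; 8.2 event-free dropouts are removed.

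**Step 4: precision, 100 children, 15%/15%.** The standard error is 5.3 points for completers only (binomial) against 5.2 with censoring (Greenwood) at true 40%, and 4.3 against 4.2 at true 20%.

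**Step 5: what censoring does not cure.** Suppose half the children have three times the hazard of the rest, with overall F = 40%. With loss of 30% in the high-risk half, 10% in the low-risk half and 10% after the event, censored Kaplan-Meier gives 38.8% and completers-only 39.9%. With 40% loss after the event instead, they give 38.8% and 35.5%.

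**The case against.** The best defence is that nobody would apply the rule this way. Section 2.2 is introduced for the primary comparison. Several of its items (combining the 36- and 37-month results, confirming failure, adjusting for confounders) cannot operate on 3.1, which has neither a failure status nor a group comparison. The import in 3.0 can therefore be read as applying only where relevant. Sections 3.2 to 3.6 are all 36-month endpoints, for which Table 1 makes sense, and naming Kaplan-Meier itself implies censoring. This stands as evidence of intent. It does not remove the conflict: Table 1 and its footnote name secondary analyses without qualification, and 3.1 nowhere withdraws them.

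A second defence is that at-risk populations and censoring rules are commonly left to the protocol, which is not at hand. That would answer a complaint about missing detail. Here the SAP does state a population rule, and it points the wrong way for this estimator.

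A third is that the bias mechanism is inferred. Section 2.4 says "Prescribing or withholding treatment may influence a parent’s decision to keep their child enrolled in the study", but as a caution about the imputation model and about differences between regimens. Bias in a within-group rate requires retention to change with deterioration inside that group. This is plausible under observation, where children are those "who are prescribed glasses either immediately or only after pre-specified deterioration" criteria are met, so deterioration brings glasses. But the SAP does not assert it and gives no size. That limit stands, as does the first example in step 5, where the completers-only figure happens to lie nearer the truth.

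A reader might go further and infer that the plan means to exclude non-completers from 3.1, that the trial's deterioration rates are therefore biased, or that the treatment comparison is compromised. The document supports none of these. The wording of 2.2 suggests the exclusion was not meant for 3.1, the SAP does not show how the analysis was run, bias needs loss related to deterioration, and 3.1 makes no group comparison.

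**Conclusion.** The conflict between the stated population rule and the chosen estimator is real on the text, and probably inadvertent. If the rule was followed, the effect is no bias and a standard error about 0.1 point larger when loss is unrelated to deterioration. When loss does depend on deterioration, the bias can go in either direction: about 1 point for modest differences in loss, and several points only under strong ones (−4.2 to +4.1 points at true 40% in the cases shown). These sizes rest wholly on assumed deterioration and loss rates. Only a descriptive secondary estimate is affected; the primary test and the 36-month secondary endpoints are not. Severity: COULD.

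**What to change.** State in 3.1 that the 36-month completion and window exclusions of 2.2 and Table 1 do not apply to this analysis, and that all randomized subjects are included, with those who do not deteriorate censored at their last visit at which deterioration was assessed. Add a matching note to Table 1. Report with the result that censoring assumes non-informative loss before the event.

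The cost is a short addition to 3.1 and a table note. A rerun on existing data is needed only if completers alone were used. If the change follows review of outcome data, mark it so, as the version table asks.

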3.1 Deterioration in Observation and Glasses Groups

For each treatment group, the Kaplan-Meier estimate of the cumulative proportion of subjects meeting deterioration criteria will be calculated along with the corresponding confidence interval. The deterioration rate in the observation group is expected to be higher than that of the glasses group, so deterioration rates will not be compared between treatment groups.

For the purposes of this analysis, a visit is defined by its corresponding analysis window. If deterioration criteria were met at a visit other than one specified by the protocol, the analysis window in which the subject met deterioration criteria will be defined as the visit at which deterioration criteria were met.

3.2 Best Distance Visual Acuity at 36-Months

A treatment group comparison of the best distance visual acuity (logMAR) in the better-seeing eyes at 36 months post-randomization will be performed using analysis of covariance (ANCOVA) models. A similar analysis will be performed to compare visual acuity in the worse-seeing eye between treatment groups. Both analyses will adjust for age at the 36-month exam and visual acuity in the eye at enrollment.

Best distance visual acuity in each eye is defined as the minimum logMAR visual acuity between measurements reported with and without trial frames, during initial assessment and retest, if required. If no retest is required at 36 months, best visual acuity is the minimum of logMAR visual acuities reported with trial frames and without trial frames during the initial assessment. If a retest is required at 36 months, best visual acuity is the minimum of logMAR visual acuities reported with and without trial frames, during the initial assessment and retest at 36 months. If a 37-month visit is required, best visual acuity is the minimum of logMAR visual acuities reported during initial assessment and retest without trial frames at the 36 months and during initial assessment with trial frames at the 37 months, if no retest is required at 37 months. If a retest is required at 37 months, best distance visual acuity is the minimum of logMAR visual acuities reported during initial assessment and retest without trial frames at 36 months and initial assessment and retest with trial frames at 37 months.

The better-seeing eye at 3 years will be defined as the eye with the smaller best logMAR visual acuity at 3 years.

For the purposes of this analysis, a value of 1.7 will be assigned to eyes that have a visual acuity worse than 20/800.

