24 criteria (below) at 36 months post-randomization. The primary analysis will be performed
25 separately for each of the two primary cohorts.

26
27 The null hypothesis of no difference between the treatment groups will be rejected if the
28 proportion meeting failure criteria in immediate glasses is significantly lower or higher than the
29 proportion in observation, based on the Barnard's exact test with 2-sided type I error of
30 $\alpha=0.05$.

31
32 Although Fisher's exact test was initially proposed, this was changed to Barnard's exact test to
33 allow for the calculation of a confidence interval on the difference between proportions, which is
34 consistent with the p-value from the test.

35
36
37 **2.1 Primary outcome**

38 At the 36-month outcome visit, each subject's condition will be classified as either failure or not
39 failure as follows:

40
41 Failure = ANY of the following criteria are met at the masked 36-month visit both with and
42 without correction in trial frames (without prism or bifocal):

- 43
- 44 1. Any measurable heterotropia in primary gaze in the distance (3 meters) or at near (1/3
45 meter) not correctable with distance refractive correction alone
 - 46 2. Strabismus surgery prior to the 36-month outcome exam
 - 47 3. Visual acuity below age norms in either eye
48 a. To be below age-normal, visual acuity in the eye must fall below age-normal
49 values on both test and retest, both with and without correction.
50 b. Visual acuity will be obtained for each eye.
 - 51 4. ≥ 2 logMAR lines of IOD if visual acuity is 20/25 or worse in the better eye (applies to
52 IOD either with or without correction but not one eye with and one eye without)
 - 53 5. ≥ 3 logMAR lines of IOD if visual acuity is 20/20 or better in the better eye (applies to
54 IOD either with or without correction, but not one eye with and one eye without)
 - 55 6. Stereoacuity at near by Randot Preschool test below age normal values

56
57 Not Failure = NONE of the criteria for failure are met

58
59 If a subject meets any failure criteria (with the exception of strabismus surgery prior to the 36-
60 month outcome exam), the visual condition that is considered to be failed must be retested by the
61 masked examiner (*section 3.6.1*) using the same procedures outlined in *section 3.6.1* of the
62 protocol. The subject must be given a 10-minute break prior to retesting each failed criterion.

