3.5 Best Near Stereoacuity at 36 Months

A treatment group comparison of best stereoacuity (log arcseconds) will be performed using an ANCOVA model, adjusting for age at the 36-month examination and the magnitude of anisometropia (using the most recent cycloplegic refraction).

Best near stereoacuity is defined as the minimum stereoacuity between measurements reported with and without trial frames, during initial assessment and retest, if required. If no retest is required at 36 months, best stereoacuity is the smaller of the measurements reported with and without trial frames during the initial assessment. If a retest is required at 36 months, best near stereoacuity is the minimum of measurements reported with and without trial frames, during initial and retest at 36 months. If a 37-month visit is required, best near stereoacuity is the minimum of measurements reported for initial assessment and retest without trial frames at 36 months and the initial assessment at 37 months, if no retest is required at 37 months. If a retest is required at 37 months, best near stereoacuity is the minimum of measurements reported during initial assessment and retest without trial frames at 36 months and initial assessment and retest with trial frames at 37 months.

For the purposes of this analysis, a value of 1600 will be assigned to participants with no detectable stereoacuity (nil).

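### Sections 3.2 and 3.5 make the best value depend on a 37-month visit being required rather than completed, so a missed visit can leave only uncorrected 36-month readings

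*SAP*

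**What the plan says.** **How the visit arises.** Under SAP section 2.1, "If failure is confirmed and the subject requires a change in glasses", the child is examined again about four weeks later in the new glasses, and uncorrected testing is not repeated. An acuity failure needs sub-normal "values on both test and retest, both with and without correction". The other non-surgical criteria also need confirmation by retest.

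**How best is defined.** Section 3.2 opens with a general rule: "Best distance visual acuity in each eye is defined as the minimum logMAR visual acuity between measurements reported with and without trial frames", over initial test and any retest. It then takes cases. For a 36-month retest: "If a retest is required at 36 months, best visual acuity is the minimum of logMAR visual acuities reported with and without trial frames", over both tests. For the 37-month case: "If a 37-month visit is required, best visual acuity is the minimum of logMAR visual acuities reported during initial assessment and retest without trial frames". Those tests are the 36-month ones, and the trial-frame readings taken at 37 months are added to them. Section 3.5 follows the same pattern: "If a 37-month visit is required, best near stereoacuity is the minimum of measurements reported for initial assessment and retest without trial frames". Those again come from the 36-month visit, and the 37-month readings are added to them.

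**Who is analysed.** Table 1 has separate columns for the 37-month visit being required and being completed. The row for an in-window 36-month visit with a required but uncompleted 37-month visit is marked as included in the primary and secondary analyses. Section 3.0 applies section 2.2 to the secondary analyses. Section 2.2 item 3 says that "subjects who complete the 36-month visit will not be considered to have met failure criteria for a condition if a required test or retest" is lacking. Section 5.1 uses 37-month data when that visit took place.

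**The concern.** The 37-month sentences take effect once the visit is required. They then stop listing the corrected 36-month readings, because corrected 37-month readings are meant to replace them. If the child does not return, there is no replacement, and only uncorrected readings remain in the minimum. Corrected readings from 36 months may exist but go unused.

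The best values feed several analyses: the ANCOVAs in 3.2 and 3.5, the age-normal proportions in 3.3 and 3.6, the interocular difference in 4.1 and the predictor models in 4.4. In moderate hyperopes, a value taken without correction may not be the child's best. The version history says that version 3.0 redefined best to bring secondary results into line with the primary analysis, so a discordance left by this wording bears on that purpose.

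**Working it through.** The SAP states no figure on this point, so the check sets the sentences side by side and works through the logic.

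**Step 1. Readings that enter the minimum (3.2; 3.5 has the same structure).**

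| Sentence | 36-month uncorrected | 36-month corrected | 37-month corrected |
|---|---|---|---|
| General definition | yes | yes | not addressed |
| No 36-month retest needed | initial | initial | none |
| 36-month retest needed | initial and retest | initial and retest | none |
| 37-month visit required | initial and retest | not listed | initial, and retest if needed |

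If the visit is required but missed, the last cell of the bottom row is empty. Taken alone, that row leaves the uncorrected 36-month readings. The row above it can also describe the same child, because a confirmed non-surgical failure needs a 36-month retest. It would keep the corrected readings.

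**Step 2. Wording elsewhere in the SAP.** Section 2.2 item 5 and section 5.1 both make use of 37-month data depend on its having been collected. Section 2.3 item 2 lets 37-month trial-frame readings replace 36-month ones only for an assessment that was failed. Sections 3.2 and 3.5 carry neither condition.

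**Step 3. When the age-normal classification changes.** Code five yes/no facts at 36 months: corrected acuity normal, uncorrected acuity normal, corrected stereoacuity normal, uncorrected stereoacuity normal, and a confirmed failure on another criterion (heterotropia or interocular difference). Acuity or stereoacuity fails only if it is below norm both with and without correction. Assume a glasses change and a missed 37-month visit.

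- All patterns: 2^5 = 32.
- Patterns with no confirmed failure: 3 × 3 × 1 = 9. Patterns that trigger the visit: 32 − 9 = 23.
- The acuity classification changes only if corrected acuity is normal and uncorrected acuity is below norm. Acuity has then not failed, so the trigger must be another failure (4 stereoacuity patterns) or stereoacuity alone (1 pattern): 4 + 1 = 5.
- Corrected acuity is normal in 10 of the 23 patterns: 5 are scored below normal and 5 stay normal.
- By symmetry, stereoacuity also changes in 5. One pattern changes both, so 5 + 5 − 1 = 9 of 23 change at least one classification.
- In none of the 9 is the changed measure itself the failed one, since a confirmed failure means its corrected readings were below norm too.

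These are counts of logical patterns, not of children.

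**Step 4. Continuous values.** The effect here is wider. Whenever the corrected 36-month reading is better than the uncorrected one, dropping it worsens the value, even on the measure that triggered the visit. Hypothetical case: stereoacuity alone failed, acuity is 20/20 (0.0 logMAR) in trial frames and 20/40 (0.3 logMAR) without. Best acuity becomes 0.3 instead of 0.0, a difference of three lines. If, purely as an assumption, 1% to 5% of an arm were such children, the arm mean would move by 0.3 × 0.01 = 0.003 to 0.3 × 0.05 = 0.015 logMAR. Whether 20/40 is below norm cannot be said, because the SAP does not list the age norms.

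**Step 5. Against the primary analysis.** In the Step 4 case the primary analysis records no acuity failure, since failure needs sub-normal acuity with correction as well. If 20/40 is below the child's norm, section 3.3 under the literal reading scores the same child as not age-normal.

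**The case against.** The strongest reply is that the text is ambiguous rather than wrong. The general definition and the 36-month-retest sentence keep the corrected readings. The 37-month sentences divide on whether a retest was needed at that visit, which presupposes attendance. Sections 2.2 item 5 and 5.1 use 37-month data only if collected. A programmer could reasonably fall back on the retest sentence. That stands as far as it goes, but nothing in the SAP directs the fallback. If the retest sentence applied generally to children sent to 37 months, it would conflict with the 37-month sentence even when the visit was completed. Two programmers could derive different values for the same child.

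Second, replacing corrected 36-month readings with 37-month ones is deliberate and mirrors section 2.2 item 2 for the primary outcome. That also stands. Only the missed visit is at issue.

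Third, a reader might infer that any child with normal corrected acuity or stereoacuity who misses the visit is scored below normal. The documents do not support this. The score is made in 3.3 and 3.6, not in 3.2 and 3.5, and it changes only under the conditions in Step 3. A reader might also infer that the treatment comparison is biased. That would need missed visits to differ by arm, on which the SAP says nothing.

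**Conclusion.** The point holds in limited form. Sections 3.2 and 3.5 condition on the wrong event, and their literal wording discards corrected 36-month readings for a child whom Table 1 expressly retains.

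- **Continuous outcomes (3.2, 3.5) and their reuse in 4.1 and 4.4:** values can be worse than the child's recorded best. For the interocular difference in 4.1 the direction is not fixed, because both eyes may change.
- **Age-normal proportions (3.3, 3.6):** a child can be wrongly scored below normal, but only with a confirmed failure on a different criterion, a glasses change, a missed 37-month visit and a below-norm uncorrected reading on the measure concerned.
- **Primary analysis:** not affected, as it does not use the best values.

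The size is unknown and may be nil, since the SAP gives no count of missed 37-month visits. The percentages in Step 4 are hypothetical.

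**What to change.** In 3.2 and 3.5, make the current 37-month text apply when the visit is required *and completed*. Then add: *if a 37-month visit is required but not completed, best acuity (or stereoacuity) is the minimum of all 36-month readings, with and without trial frames, initial and retest.* Carry this definition into 3.3, 3.6, 4.1 and 4.4, and check it against Table 1 and section 2.2 item 3. Reporting the number of required but missed 37-month visits by arm and cohort would settle the size.

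The cost is about one sentence in each of two sections and a small programming change. The retained corrected reading may be in an outdated prescription and so understate what the child can see. It cannot give a worse value than the literal rule, because a minimum over more readings is never larger.

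The change removes the misscore only for measures that did not trigger the visit. For the triggering measure, every 36-month reading is below norm, so 3.3 or 3.6 will still score the child below normal. The primary analysis, under section 2.2 item 3 and Table 1 footnote a, will not count a failure on that measure, because the required 37-month test was not done. That difference remains and should be acknowledged in the text.
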